- Changes in the QoL of patients suffering from acute or chronic hemorrhoids, who received conservative treatment, within 1 month after presenting to a doctor.
- Changes in the QoL of patients suffering from acute or chronic hemorrhoids, who received combination treatment, within 1 month after presenting to a doctor.
- Changes in the QoL of patients suffering from acute or chronic hemorrhoids, who underwent minimally invasive interventions, within 1 month after presenting to a doctor.
- Changes in clinical manifestations in patients suffering from acute or chronic hemorrhoids, and their association with demographic and clinical parameters, as well as the chosen treatment strategies (surgical, minimally invasive, or conservative).
- Patient's compliance with recommendations of a doctor.

Design:

The EQUALISER program is a Russian, multicenter, observational program.

In Russia, the program is scheduled for 2018-2019. It is expected that 90 doctors will take part in the program in 60 cities of the Russian Federation. The planned number of patients is 900. Each participating doctor includes at least 10 patients and fills out an electronic case report form (CRF). All treatment is carried out in accordance with the instructions for medical use and routine clinical practice.

| | |
|------------------------------------|---------|
| First visit of the first patient | 02/2019 |
| Last visit of the last patient | 05/2019 |
| Completion of statistical analysis | 08/2019 |
| Preliminary report | 12/2019 |
| Final report | 03/2020 |

Methods:

During the program, at each visit the leading clinical symptoms of hemorrhoids will be assessed.

The quality of life assessment will be carried out using the validated questionnaire SF36 (in Russian) (**Appendix 2**)

Inclusion visit (V0)

Patients who meet the inclusion criteria will be included in the program, and for them the CRF will be completed.

Visit 1 (V1) Surgical intervention (if applicable).

Visit 2 (V2) in 5-7 days after surgical intervention or 5-7 days after the Inclusion Visit (V0), if intervention was not performed.

Visit 3 (V3) in 25-30 days after surgical intervention or 25-30 days after Inclusion Visit (V0), if intervention was not performed.

| Visit | Actions |
|-------|---|
| V0 | 
 • Signing the Informed Consent Form |

| | |
|----|--|

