- 5) Patients with inflammatory bowel diseases (Crohn's disease, non-specific ulcerative colitis);
- 6) Patients with concomitant diseases of the anal canal (fissure, fistulas, paraproctitis, etc.);
- 7) Patients taking anticoagulants;
- 8) Patients with previous anorectal surgeries, including hemorrhoidectomy or excision of anal fistula.

Treatment

The observational nature of program presumes that all examinations, procedures and changes in the treatment of patients, including changes in the dosing regimen, should be carried out only on the basis of judgment of the treating physician and in full compliance with the guidelines on the treatment of patients of the analysed population, instructions for medical use of drugs, and in the settings of daily routine practice.

Therapy is conducted in full accordance with existing guidelines. The patient's participation in the program, as well as his/her refusal to continue such participation, should not affect the current treatment, the availability of diagnostic procedures or the volume and quality of other necessary medical care.

Safety considerations

1. Definitions

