- Change in the proportion (in %) of patients with bleeding events or prolapse of hemorrhoids among patients suffering from acute or chronic hemorrhoids, within 1 month after presenting a doctor, and its relationship to demographic, clinical parameters and the chosen treatment strategies (surgical, minimally invasive, and conservative).
- Proportion (%) of patients compliant with recommendations on lifestyle changes
- Proportion (%) of patients compliant with recommendations on medical therapy.

Statistical analysis:

Baseline characteristics will be analyzed in all included patients despite adherence to the protocol. Analysis of the results of program will be performed using the SPSS 12.0 software package (SPSS Inc., USA). The data entry errors will be corrected before the statistical processing. Quantitative parameters will be presented depending on the distribution of primary data as arithmetic mean \pm standard deviation for parametric variables, or as median (25; 75 percentiles) for nonparametric variables. Multiple comparisons will include adjustments for continuity.

Changes in the quantitative parameters during the follow-up period will be evaluated using the Student's t-test for paired samples or its nonparametric analogue, Wilcoxon test. Differences on the quantitative parameters, both between the independent groups and during the follow-up, will be evaluated as the mean difference with the corresponding 95% confidence interval.

Comparisons of changes on the VAS scales and the Rome III constipation scale will be carried out using two-factor analysis of variance (ANOVA) with repeated measures to compare the scores before and after the treatment.

Adverse events will be recorded and analyzed in patients with the reporting of all the AEs, SAEs, ADRs, SADRs and special situations.

Administrative considerations

The right to own the documentation, data and results of the program.

The sponsor reserves the exclusive rights for all materials, information, unpublished documentation, results and information received during the program. The sponsor reserves the right to send data on the program (case report forms, results of analyses, and reports) to health authorities.

No unpublished documentation or information transmitted to investigators can be transferred to unauthorized persons without the prior written consent of the Sponsor.

Publication and communication

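### The analysis makes no allowance for clustering by doctor; if one-month change is positively correlated within doctor, intervals for overall and within-strategy changes, and for comparisons that follow the doctor, are too narrow

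*Combined protocol and SAP*

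**What the plan says.** The 'Design' section sets out a nested sample. On recruiting sites it says: "It is expected that 90 doctors will take part in the program in 60 cities of the Russian Federation". The target sample size follows in its own sentence: "The planned number of patients is 900". The cluster size comes from the recruitment rule that "Each participating doctor includes at least 10 patients". The 'Treatment' section adds that examinations, procedures and treatment changes "should be carried out only on the basis of judgment of the treating physician", in line with guidelines and product instructions.

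The 'Statistical analysis' section is the whole analysis plan. Change over follow-up is tested with the Student "t-test for paired samples or its nonparametric analogue, Wilcoxon test". Differences in such measures, "both between the independent groups and during the follow-up, will be evaluated as the mean difference with the corresponding 95% confidence interval". VAS and constipation scores are compared by "two-factor analysis of variance (ANOVA) with repeated measures to compare the scores before and after the treatment".

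The only dependence these methods handle is repeated measurement in the same patient. No doctor, centre or city effect is named, nor a mixed model, GEE, robust variance or ICC. The sentence on continuity adjustments for multiple comparisons does not deal with clustering.

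**The concern.** The standard errors behind a paired t-test, an unpaired mean difference and a patient-level ANOVA assume that one patient's change carries no information about another's. Here one doctor examines, treats, advises and completes the case report form for about 10 patients. It is plausible that some doctors' patients improve more than others', through technique, choice of regimen or quality of advice. If so, the 900 changes hold less information than 900 independent ones.

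The primary endpoint, change in quality of life within one month, is exposed even though no groups are compared, so this is a separate matter from confounding by treatment choice. At stake is the honesty of the reported 95% intervals and p-values for the overall change, for the change under each strategy, and for any strategy comparison that is largely a comparison between doctors.

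**Working it through.** **Inputs from the documents ('Design').** 90 doctors, 900 patients, 60 cities. 90 × 10 = 900 reproduces the planned total, with mean cluster size m = 900/90 = 10. This is recruitment arithmetic only: no power calculation, SD or ICC is given, so there is no stated precision to reproduce.

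**Assumed input.** The ICC of the one-month change within doctor, taken over 0.01 to 0.10. This is the correlation of the change, not of the score at a single visit.

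**Formulas**, for the overall mean change or a contrast in which every patient of a doctor falls in the same group:
- design effect DEFF = 1 + (m − 1) × ICC
- effective n = 900 / DEFF
- factor by which the correct interval is wider = √DEFF
- actual two-sided error at nominal 5% = 2 × [1 − Φ(1.96/√DEFF)]
- correct half-width in SDs of the change = 1.96 × √(DEFF/900)

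Worked case, ICC 0.05: DEFF = 1 + 9 × 0.05 = 1.45; effective n = 900/1.45 = 621; √1.45 = 1.20; error = 2 × [1 − Φ(1.96/1.204)] = 10.4%.

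| Assumed ICC | DEFF | Effective n | Interval factor | Actual error | Half-width (SD) |
|---|---|---|---|---|---|
| 0 | 1.00 | 900 | 1.00 | 5.0% | 0.065 |
| 0.01 | 1.09 | 826 | 1.04 | 6.0% | 0.068 |
| 0.02 | 1.18 | 763 | 1.09 | 7.1% | 0.071 |
| 0.05 | 1.45 | 621 | 1.20 | 10.4% | 0.079 |
| 0.10 | 1.90 | 474 | 1.38 | 15.5% | 0.090 |

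Half-widths stay in SD units because the documents give no SD from which to convert them to points.

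**Contrast balanced within doctors.** If each doctor's patients split 50:50 between two groups and the doctor effect is the same in both, it cancels from the difference and DEFF = 1 − ICC. At ICC 0.05, DEFF = 0.95 and the actual error is 4.4%: the planned interval is slightly too wide.

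**Subgroups.** If three strategies split evenly within each doctor (an assumption), m for one strategy is 10/3 ≈ 3.3. At ICC 0.05, DEFF = 1 + 2.33 × 0.05 = 1.12 and the error for that strategy's mean change is about 6.4%, not 10.4%.

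**Simulation check.** 20,000 data sets of 90 × 10 normal changes at ICC 0.05 gave rejection rates of 10.3% for the paired test, 10.3% for a comparison between doctors and 4.3% for a comparison split evenly within doctors, in agreement with the formulas.

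**The case against.** Several points on the other side are sound and set the limits of this one.

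- A reader might infer that every test and interval is too narrow. The working shows otherwise: contrasts balanced within doctors are about right or slightly conservative. Demographic groups may well mix within a doctor's list.
- A reader might infer that strategy is chosen mainly at doctor level. No passage says so. The 'Introduction' ties surgery to grades III–IV and conservative treatment to grades 1–2, which is a patient-level factor, and the mix of strategies per doctor is not given.
- A reader might take 'independent' in the quoted sentence as a claim that the 900 patients are independent. It means unpaired groups. The plan omits clustering; it does not deny it.
- Pairing removes doctor effects that are additive and stable over time, such as diagnostic habits or the way a scale is explained. Only doctor-to-doctor variation in improvement inflates the error, and its size is unknown.
- This is an observational program with no stated hypothesis or decision rule, so a modestly narrow interval costs less than it would in a confirmatory trial.

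The omission itself remains. The tests named require independence whether or not the plan says so, and pairing does not remove variation between doctors in how much their patients improve.

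**Conclusion.** The point holds in conditional form. As written, the plan understates uncertainty for the overall and within-strategy changes, and for comparisons that follow the doctor, whenever one-month change is positively correlated within doctor. With 10 patients per doctor and an assumed ICC of 0.01 to 0.10, the loss runs from slight (interval 4% too short relative to the planned width, error 6.0%) to material (38%, error 15.5%). At ICC 0 nothing changes.

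These figures rest on the assumed ICC, equal cluster sizes and a normal approximation; the documents supply only the counts. They do not settle where in the range the program will fall, nor which strategy comparisons run between doctors and which run within them. Shared city effects could add to the problem (mean 900/60 = 15 patients per city; DEFF 1 + 14 × 0.05 = 1.70 at an assumed city ICC of 0.05), but nothing in the documents gives their size.

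**What to change.** In 'Statistical analysis', state that confidence intervals and p-values for each change and each strategy comparison will be based on doctor-clustered standard errors, or on a linear mixed model for the change score with a random intercept for doctor. If visit scores are modelled instead of the change, the doctor effect must be allowed to differ by visit, since a constant one cancels from the change. For proportions such as bleeding, prolapse and compliance, use GEE or a logistic mixed model clustered by doctor. Report the estimated ICC. A separate city level is optional: with 90/60 = 1.5 doctors per city on average, its variance would be hard to tell apart from the doctor variance.

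Two things need confirming. The doctor identifier must be kept in the analysis dataset; each doctor fills out the form, but its fields are not shown. The software must support these methods, and the plan names only SPSS 12.0.

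The cost is somewhat wider intervals and a little more analysis work. No extra patients, visits or measurements are needed.

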| | 
 • Checking of fulfilment of inclusion/non-inclusion criteria. • Obtaining the data: 
 - Disease duration - Clinical manifestations of haemorrhoids - клинические проявления геморроя: 
 • prolapse of hemorrhoids (Appendix 4) • pain, itching, dyscomfort (Appendix 6) • bleeding - The Rome III criteria for constipation (Appendix 3) - Conservative treatment (systemic venotonic drug, topical agents, analgetics) - Diagnosis according to the National guidelines on coloproctology, 2015 (Appendix 5) - The surgical treatment scheduled - QoL assessment using the SF36 scale (Appendix 2) |
| V1 | 
 • Surgical treatment (if performed) |
| V2 | 
 • 5-7 days after intervention or after V0, if intervention was not performed • Clinical manifestations of haemorrhoids at the day of visit • Patient's compliance with doctor recommendations • Recording the adverse events (Appendix 1). • Assessment of pain, itching, and discomfort using VAS (Appendix 5) |
| V3 | 
 • 25-30 days after intervention or after V0, if intervention was not performed • Clinical manifestations of haemorrhoids at the day of visit • Patient's compliance with doctor recommendations • Patient's satisfaction with the treatment • Recording the adverse events • Clinical manifestations of haemorrhoids at the day of visit • QoL assessment using the SF36 scale |

Inclusion criteria

Patients fulfilment of the criteria of the inclusion in the program will be determined by the following parameters:

- 1) Age over 18 years;
- 2) Providing written information to a patient about inclusion in the program, and his/her consent to participate in it;
- 3) Absence of conditions requiring urgent medical care and not related to hemorrhoids;
- 4) The patient was diagnosed with:
 - Acute hemorrhoids (with thrombosis of hemorrhoids);
 - Exacerbation of chronic hemorrhoids (pain, bleeding, oedema (swelling) of hemorrhoids);
 - Chronic hemorrhoids (prolapsed hemorrhoids, bleeding events, anal discomfort).

Exclusion criteria

- 1) The patient is consulting for an urgent issue not related to hemorrhoids;
- 2) The presence of severe systemic diseases;
- 3) Pregnancy;

- 4) Inability to understand the meaning of the Program and follow the doctor's recommendations

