APPENDIX 3. The Rome III diagnostic criteria for the constipation

| Symptoms | Characteristics of the symptoms |
|---|---|
| 1. Straining during at least 25% of defecations | Symptoms should be observed within 12 weeks (not necessarily consecutive) during the previous year. |
| 2. Lumpy or hard stools in at least 25% of defecations | Syndrome must include two or more of the symptoms listed in this table. |
| 3. Sensation of incomplete evacuation for at least 25% of defecations | |

| | |
|---|--|
| 4. Sensation of anorectal obstruction/blockage for at least 25% of defecations | |
| 5. Manual maneuvers to facilitate at least 25% of defecations (e.g., digital evacuation, support of the pelvic floor) | |
| 6. Fewer than three defecations per week | |

APPENDIX 4

Classification of internal hemorrhoids (Goligher's classification)

*Assessment criteria:

- Grade I Hemorrhoids are prolapsed only into the anal canal.
- Grade II Bleeding and prolapse of hemorrhoids. Hemorrhoids spontaneously reduce after defecation.
- Grade III Prolapse of hemorrhoids after defecation requires their manual reduction.
- Grade IV Prolapse of hemorrhoids that cannot be reduced into the anal canal.

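### The planned before/after ANOVA on Rome III constipation cannot be run: the criteria are recorded only at V0 and have no defined score; VAS at V3 is implied but not named

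*Combined protocol and SAP*

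**What the plan says.** The Statistical analysis section gives one sentence to this method: "Comparisons of changes on the VAS scales and the Rome III constipation scale will be carried out using two-factor analysis of variance (ANOVA") in its repeated-measures form, with the stated aim of comparing scores before treatment with scores after it.

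For Rome III, the visit table under Methods has one entry, at V0: "The Rome III criteria for constipation (Appendix 3"). It is a data item of its own, apart from the clinical manifestations of haemorrhoids (prolapse; pain, itching and discomfort; bleeding). It does not appear at V2 or V3. Appendix 3 lists six symptoms and two conditions: "Symptoms should be observed within 12 weeks (not necessarily consecutive) during the previous year", and "Syndrome must include two or more of the symptoms listed in this table".

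For VAS, the V0 row has "pain, itching, dyscomfort (Appendix 6") as a sub-item of the clinical manifestations. The V2 row has the clinical manifestations and, as a separate item, a VAS assessment. The V3 row prints the clinical-manifestations line twice and does not mention VAS. The general rule under Methods is: "During the program, at each visit the leading clinical symptoms of hemorrhoids will be assessed". The Variables list includes a change in CRF-recorded VAS for pain, itching and discomfort within one month.

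**The concern.** A before/after comparison needs the same quantity measured at least twice, and an ANOVA needs that quantity to be numeric. On the documents' own description Rome III meets neither condition. An analyst following the plan would have to drop the analysis without saying so, or improvise a score and a second time point after the data are in.

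The VAS question is different in kind. A 1-month VAS change is a listed variable and supports a secondary endpoint: "Changes in clinical manifestations in patients suffering from acute or chronic hemorrhoids, and their association with demographic and clinical parameters". A site that reads the V3 row literally, noticing that V2 asks for VAS in addition to the clinical manifestations and V3 does not, could omit it. The only follow-up VAS would then be the V2 value at 5 to 7 days. A symptom score for the day of the visit cannot be recovered later.

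**Working it through.** The plan gives no figure to reproduce here, so the check sets the analysis sentence against the visit table and the appendices.

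**1. Number of Rome III measurements.** Scheduled at V0: yes. At V2: no. At V3: no. Total = 1. Degrees of freedom for the within-patient time factor = assessments − 1 = 1 − 1 = 0. The symptom items at V2 and V3 do not fill the gap, because V0 lists Rome III separately from the haemorrhoid manifestations.

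**2. Type of measurement.** Appendix 3 gives a threshold (at least 2 of 6 symptoms) and a duration condition (12 weeks within the previous year). It gives no weights, total or range. The result as defined is binary.

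**3. Would repeating it at V3 rescue the analysis?** V3 timing under Methods: "Visit 3 (V3) in 25-30 days after surgical intervention or 25-30 days after Inclusion Visit (V0), if intervention was not performed".

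*Non-operated patients.* The look-back window moves forward by 25 to 30 days.
- New share of the year: 25/365 = 6.8%; 30/365 = 8.2%. The two windows share 93.2% to 91.8% of their days.
- Shift in weeks: 25/7 = 3.6; 30/7 = 4.3.
- With the 30-day shift, going from not met to met needs at least 12 − 4.3 = 7.7 qualifying weeks at V0. Going from met to not met needs fewer than 12 + 4.3 = 16.3. Outside about 7.7 to 16.3 weeks the status cannot change, whatever the treatment does.

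*Operated patients.* The V0–V3 gap is w + 25 to w + 30 days, where w is the wait from V0 to surgery. The documents do not give w. Assumed values:

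| Assumed w (days) | New days | Share of 365 |
|---|---|---|
| 0 | 25–30 | 6.8%–8.2% |
| 14 | 39–44 | 10.7%–12.1% |
| 30 | 55–60 | 15.1%–16.4% |
| 60 | 85–90 | 23.3%–24.7% |

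The longer waits sit badly with endpoints defined within one month of presentation. Taking a month as 30 days, V3 at 25 to 30 days after surgery leaves room for only 30 − 30 = 0 to 30 − 25 = 5 days of waiting, so operated patients would be close to the first row.

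**4. VAS by visit.** V0: through Appendix 6. V2: named. V3: not named, but implied by the each-visit rule, by the clinical-manifestations line (which at V0 contains the VAS symptoms) and by the 1-month variable. VAS is therefore named at 1 of 2 follow-up visits, and V3 is ambiguous rather than absent. A V0-to-V2 comparison is possible as scheduled.

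**5. Related slips.** The V2 row sends the reader to Appendix 5 for the VAS; Appendix 5 is the diagnosis wording and the VAS is Appendix 6. Appendix 6 records cm and the Variables list uses mm. This is a fixed factor of 10 and does not affect any test.

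**The case against.** The strongest reply accepts the Rome III mismatch and disputes its weight. No endpoint or listed variable concerns a change in constipation, so what fails is one phrase about a non-endpoint. A 0-to-6 symptom count could be built from Appendix 3. The look-back arithmetic describes a repeat measurement that the plan does not propose. VAS at V3 can be inferred from three places, the doubled line may be a drafting slip, and the eCRF, which is not among the documents, may already contain the field. The plan also has paired t and Wilcoxon tests that would cover VAS change. Finally, a short-recall constipation measure at V3 would be another legitimate repair, and the plan names no covariate-adjusted model in which baseline constipation could be used.

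Much of this is fair and limits the point. It is right that no endpoint is lost, that the VAS issue is a clarification, and that the look-back figures show only why the obvious repair is poor. The symptom count does not help: the plan does not define one, and even a count would have no second value. Nor do the paired tests create a V3 VAS where a site did not collect one. Baseline constipation does have a place without a new model, because the secondary endpoints already ask for associations with clinical parameters, which a subgroup display can serve.

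**Conclusion.** The concern holds. The Rome III change analysis cannot be carried out as written: 1 of the 2 required measurements is scheduled, and the instrument as defined yields met or not met, with no score. This follows from the documents alone and needs no assumption. That a V3 repeat would be of little use rests on the stated 25-to-30-day timing in non-operated patients (6.8% to 8.2% of the look-back new). For operated patients it rests on an assumed wait (6.8% to 24.7% for 0 to 60 days).

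The VAS point is smaller. V3 collection is implied but not named, and whether any value would be lost depends on the eCRF and on how sites read the table. It still deserves correction, because it touches a listed 1-month variable and a secondary endpoint. Overall this should be corrected; it does not touch the primary endpoint.

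**What to change.** - **Statistical analysis:** delete Rome III from the before/after ANOVA. Use V0 constipation (criterion met, yes/no) as a baseline subgroup factor, or as a covariate if an adjusted model is added. If the sponsor does want to study change in constipation, that needs a different measure at V3, with a defined score and a recall period that fits the follow-up.
- **Visit table, V3:** replace the duplicated clinical-manifestations line with an explicit item for VAS assessment of pain, itching and discomfort, citing Appendix 6.
- **Clean-up:** change the V2 reference from Appendix 5 to Appendix 6, and state one VAS unit (for example, recorded in cm and multiplied by 10 for reporting in mm).

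Cost: the Rome III change is wording only and can be made at any time before the analysis, whose completion is planned for 08/2019. The VAS change is a visit-table and eCRF clarification with no extra visit, but it is time-sensitive. Visits are planned for 02/2019 to 05/2019 and the document is dated 1/03/2019. Depending on how that date is read, the clarification would reach about 90 doctors shortly before or during enrolment, and patients who complete V3 before then may lack a V3 VAS.

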- Rates (in %) of different variables of health profile according to the EQ-5D in patients suffering from acute or chronic hemorrhoids, and their relationship to demographic, clinical parameters and the chosen treatment strategies (surgical, minimally invasive, and conservative).
- Change in the mean score of the EQ-5D index in patients suffering from acute or chronic hemorrhoids, who underwent surgical intervention, within 1 month after presenting to a doctor
- Change in the mean score of the EQ-5D index in patients suffering from acute or chronic hemorrhoids, who received conservative treatment, within 1 month after presenting to a doctor
- Change in the mean score of the EQ-5D index in patients suffering from acute or chronic hemorrhoids, who received combination treatment, within 1 month after presenting to a doctor
- Change in the mean score of the EQ-5D index in patients suffering from acute or chronic hemorrhoids, who underwent minimally invasive intervention, within 1 month after presenting to a doctor

- Change in the mean score by VAS (in mm) scale from SF36 questionnaire in patients suffering from acute or chronic hemorrhoids, who underwent surgical intervention, within 1 month after presenting a doctor, in general population and in specific demographic groups
- Change in the mean score by VAS (in mm) scale from SF36 questionnaire in patients suffering from acute or chronic hemorrhoids, who received conservative treatment, within 1 month after presenting to a doctor
- Change in the mean score by VAS (in mm) scale from SF36 questionnaire in patients suffering from acute or chronic hemorrhoids, who received combination treatment, within 1 month after presenting to a doctor
- Change in the mean score by VAS (in mm) scale from SF36 questionnaire in patients suffering from acute or chronic hemorrhoids, who underwent minimally invasive intervention, within 1 month after presenting to a doctor
- Change in the mean score by VAS (in mm) scale from CRF for pain, itching, and discomfort in patients suffering from acute or chronic hemorrhoids, within 1 month after presenting to a doctor, and their relationship to demographic, clinical parameters and the chosen treatment strategies (surgical, minimally invasive, and conservative).

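### The repeated-measures ANOVA planned for VAS change pools one variance over treatment groups of unplanned size; an unequal-variance method would protect its error rate at almost no cost

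*Combined protocol and SAP*

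**What the plan says.** The Statistical analysis section names one method for change in the VAS and Rome III scores: "two-factor analysis of variance (ANOVA) with repeated measures to compare the scores before and after the treatment". Time is one factor; the other is not named. The Variables list under Statistical parameters defines the symptom outcome as the change in VAS score for pain, itching and discomfort within one month, together with "their relationship to demographic, clinical parameters and the chosen treatment strategies (surgical, minimally invasive, and conservative"). Other variables in that list treat combination treatment as a separate group, so there could be three or four strategy groups.

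The Design section sets the numbers: "The planned number of patients is 900", and "Each participating doctor includes at least 10 patients". The Treatment section leaves all treatment to the treating physician. No quota, stratification or randomisation by strategy is described.

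For this analysis the plan gives no variance check, unequal-variance test, group-specific covariance or robust standard error. The Wilcoxon option is offered for paired change during follow-up, so it does not cover a comparison between groups. The continuity adjustment mentioned for multiple comparisons does not concern variance.

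**The concern.** A standard repeated-measures ANOVA assumes that every group has the same variances and covariances. The F test tolerates unequal variances when groups are of similar size, but not when sizes differ. If the small groups are the more variable ones, it rejects too often. If the large group is the more variable one, it rejects too seldom and loses power.

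This program could meet both conditions. Strategy sizes follow routine practice. The Introduction links strategy to disease grade, and the inclusion criteria admit acute thrombosis, exacerbation and chronic disease, so the spread of change could well differ between strategies. At stake is whether a nominal 5% statement about symptom change by strategy means what it says.

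**Working it through.** **Inputs from the documents.** 90 doctors with at least 10 patients each: 90 × 10 = 900, which reproduces the planned total. No power calculation, SD, group size or alpha is given. A two-sided 5% level is assumed, consistent with the 95% intervals in the plan.

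**Assumed inputs.** Three strategy groups, splits of the 900, SD ratios from 1 to 2 in both directions, normal change scores, independent patients, and no true difference in mean change.

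**Step 1: the test.** With two visits, let d be a patient's change. The group-by-time F is

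F = [Σ nᵢ(d̄ᵢ − d̄)² / (k − 1)] / [Σ (nᵢ − 1)sᵢ² / (N − k)],

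which is a one-way F on d with one pooled variance.

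**Step 2: why it goes wrong.** With no true difference, the expected numerator is Σ(1 − nᵢ/N)σᵢ²/(k − 1), and the expected denominator is Σ(nᵢ − 1)σᵢ²/(N − k). Take 600/200/100.

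- SDs 1 : 1.25 : 1.5. Numerator: (0.3333×1 + 0.7778×1.5625 + 0.8889×2.25)/2 = 1.774. Denominator: (599×1 + 199×1.5625 + 99×2.25)/897 = 1.263. Ratio 1.40, so F is too large on average.
- SDs 1.5 : 1.25 : 1. Numerator: (0.3333×2.25 + 0.7778×1.5625 + 0.8889×1)/2 = 1.427. Denominator: (599×2.25 + 199×1.5625 + 99×1)/897 = 1.960. Ratio 0.73, so F is too small.
- Equal groups: both expressions reduce to the mean of the variances. Ratio 1.

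**Step 3: type I error at 600/200/100** (10,000 simulated programs per row, middle group given an intermediate SD):

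| SD pattern | Pooled F | Welch F |
|---|---|---|
| Equal | 5.4% | 5.4% |
| Smallest group 1.25 × largest group | 8.2% | 4.8% |
| Smallest group 1.5 × largest group | 11.6% | 4.8% |
| Smallest group 2 × largest group | 18.2% | 5.0% |
| Largest group 1.5 × smallest group | 1.9% | 4.7% |

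The simulation error near 5% is √(0.05×0.95/10,000) = 0.2 percentage points. A repeat gave 8.6%, 12.0%, 17.8% and 1.8% for the four unequal rows.

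**Step 4: other assumed splits** (40,000 runs each, SDs listed in the order of the groups):

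| Split | SDs | Pooled F |
|---|---|---|
| 300/300/300 | ratio up to 2 | 4.8–6.0% |
| 450/270/180 | 1 : 1.25 : 1.5 | 8.4% |
| 630/180/90 | 1 : 1.5 : 1.5 | 13.6% |
| 720/90/90 | 1 : 1.5 : 1.5 | 17.2% |
| 720/90/90 | 2 : 1 : 1 | 0.1% |
| 540/180/90/90 (four groups) | 1 : 1 : 1.5 : 1.5 | 13.7% |

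Welch's F stayed between 4.8% and 5.3% throughout. The visit table names the VAS at V2 and points to its appendix at V0, but at V3 lists only clinical manifestations, so the number of time points is uncertain. With three visits (4,000 runs, within-patient correlation 0.5, no sphericity correction), the 720/90/90 case with SDs 1 : 1.5 : 1.5 rises to 23.8%. A sphericity correction would not cure this, because the variance differs between groups rather than between visits.

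**Step 5: intervals, if they were pooled.** For 600 v 100 with SD ratio 1.5, the pooled variance is (599 + 99×2.25)/698 = 1.177. The pooled SE² is 1.177×(1/600 + 1/100) = 0.01374, and the true SE² is 1/600 + 2.25/100 = 0.02417. The SE ratio is √(0.01374/0.02417) = 0.754, and coverage is 2Φ(1.96×0.754) − 1 = 86%. At SD ratios 1.25 and 2 the SE ratios are 0.854 and 0.632, giving 91% and 78%.

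**The case against.** The strongest case against is that this is a textbook caution attached to an incompletely specified secondary analysis. Much of it stands.

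- *The factor is inferred.* The ANOVA sentence speaks only of scores before and after treatment, and the Variables list also mentions demographic and clinical parameters. Strategy is the natural reading, not a stated one. The missing name is itself a gap, and the same weakness would affect any unbalanced grouping factor.
- *Nothing in the documents fixes the size or direction of the error.* A reader might infer that the operated group will be small and more variable, so that false positives are expected. No passage supports either half. The Introduction calls surgery the main method for grades III–IV, and prolapsed disease is eligible. If the larger group varies more, the test is conservative.
- *The intervals are not stated to be pooled.* The plan promises mean differences with 95% intervals and names no variance estimator. The coverage figures show only what a pooled choice would do.
- *Clustering matters too.* A reader might infer that the error rate is wrong whatever is done about doctors. That does not hold. With 90 doctors × 10 patients, 600/200/100, SDs 1 : 1.25 : 1.5, strategies mixed within doctor and an assumed intraclass correlation of 0.05, a doctor-robust test gave 4.9% against 11.7% for the pooled F. It was less exact, at 9–10%, when the doctor wholly determined the strategy. In that extreme case Welch's test, which ignores doctors, gave 14%, and 21% at a correlation of 0.10.

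What remains is that the plan names a method that is sensitive to a feature the design leaves uncontrolled, and that a less sensitive method is available at almost no cost.

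**Conclusion.** The point holds as a conditional one and as a free improvement, not as a demonstrated error. Under the assumed 600/200/100 split, the pooled test runs at about 8% to 18% if the smallest group's SD is 1.25 to 2 times the largest group's, at about 2% if the largest group is 1.5 times as variable, and close to 5% if sizes or SDs are equal. These figures rest on assumed sizes and SDs, normal change scores, independent patients, and strategy as the second factor.

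A reader might take this as undermining the program's main question. The documents do not support that. The primary endpoint is change in quality of life; VAS symptoms belong to a secondary endpoint on clinical manifestations, and the ANOVA sentence covers only the VAS and Rome III scales. Nor would correcting the variance assumption make strategies comparable: physicians choose treatment by case mix, and that confounding is a separate matter.

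**What to change.** In the Statistical analysis section:

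1. Name treatment strategy as the between-patient factor, and state whether combination treatment is a level of it.
2. Replace the pooled ANOVA for VAS change with Welch ANOVA on change from V0 at each later visit where the VAS is recorded, or with a repeated-measures mixed model that has a separate covariance matrix per strategy. A model with doctor-clustered robust standard errors also tolerates unequal variances and has the advantage of addressing clustering.
3. State that between-strategy mean differences will carry unequal-variance 95% intervals.

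The cost is a few lines of wording. No extra patients or data are needed. With 900 patients the loss of degrees of freedom is negligible, and Welch's test keeps its level when the variances are equal.
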